### 4.2 Study Groups

Group 1 - ICG Group (n=112): Sentinel lymph node mapping using indocyanine green alone with near-infrared fluorescence imaging.

Group 2 - CNs Group (n=112): Sentinel lymph node mapping using carbon nanoparticles alone with visual identification.

Group 3 - ICG+CNs Group (n=112): Sentinel lymph node mapping using combined dual-tracer technique with both NIRF imaging and visual identification. This group will also undergo deep learning video analysis.

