#### 9.4.3 Model Validation

10-fold stratified cross-validation will be used:

- Data split: 90% training, 10% testing in each fold
- Stratification ensures balanced outcome distribution
- Performance metrics averaged across all folds
- Standard deviation calculated to assess stability

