### 9.5 Model Performance Metrics

The following metrics will be calculated for each model:

- Area Under the ROC Curve (AUC)
- Accuracy
- Sensitivity (Recall)
- Specificity
- Positive Predictive Value (Precision)
- Negative Predictive Value
- F1 Score
- False Positive Rate
- Lift
- Brier Score
- Kappa Coefficient
- Dice Coefficient

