### 9.6 Model Comparison

- DeLong test for comparing AUC values between models
- Probability-based model ranking approach (PMRA)
- Win-probability heatmaps
- Wald test p-value comparisons
- Decision curve analysis for clinical utility
- Calibration curves for reliability assessment
- Learning curves for overfitting assessment

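### The between-fold SD in Section 9.4.3 mostly reflects test folds of about 11 patients, so it shows neither model stability nor precision, and no confidence interval is planned for any model metric

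*Combined protocol and SAP*

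**What the plan says.** Section 4.2 restricts the video models to one group: "Group 3 - ICG+CNs Group (n=112): Sentinel lymph node mapping using combined dual-tracer technique", followed by "This group will also undergo deep learning video analysis". Section 9.4.3 sets the validation: "10-fold stratified cross-validation will be used", with "Data split: 90% training, 10% testing in each fold". Results are then combined by two rules: "Performance metrics averaged across all folds" and "Standard deviation calculated to assess stability". Section 9.5 opens with "The following metrics will be calculated for each model" and lists twelve metrics, among them AUC, PPV, NPV, F1, lift and kappa. Section 9.6 adds "DeLong test for comparing AUC values between models", together with calibration and decision curves.

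Sections 9.3.1 and 9.3.2 plan 95% confidence intervals for detection rates and for tracer accuracy. Nothing equivalent is stated for the models. The plan also does not mention pooled out-of-fold predictions, repeated cross-validation, a classification cut-off, or a rule for a fold in which a metric cannot be computed.

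**The concern.** Developing and validating the models is the third primary objective in Section 3.1. As planned, each of nine architectures would be reported as a mean of ten fold values with their SD. A reader will want to know two things: how precisely the performance is known, and whether the model would come out much the same on another split of the data.

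The SD answers neither question if it is driven mainly by having only 11 patients in each test fold. A perfectly stable model would then look erratic. A real difference between architectures, or a gain over sentinel node status alone (the secondary hypothesis), could not be told from noise using the reported summaries.

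**Working it through.** The plan gives no sample size, target AUC or precision target for the models, so there is no figure of its own to reproduce.

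**Inputs.** 112 patients (Section 4.2); ten stratified folds (Section 9.4.3). The prevalence of second-echelon and non-sentinel metastasis is not given. Section 5.4 plans on 50% for lymph node metastasis overall, and Section 2.1 cites 30% to 80% occult disease. I assume 20%, 30% and 50%, that is 22, 34 and 56 positives. I also assume a true AUC of 0.80.

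**Step 1, fold size.** 112/10 = 11.2 patients, with 2.2, 3.4 or 5.6 positives per fold. If 10% of patients are lost, the fold size is 10.1.

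**Step 2, sampling error of an AUC from a fixed score.** With m positives and n negatives, Var = [A(1−A) + (m+n−2)(Q−A²)]/(mn). Here Q is the chance that two random positives both outrank one random negative. For normal scores of equal spread and A = 0.80, Q = 0.6872 and Q−A² = 0.0472.

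- All 112 patients: the numerator is 0.16 + 110 × 0.0472 = 5.35.
- One average fold: the numerator is 0.16 + 9.2 × 0.0472 = 0.594.

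| Prevalence | mn, all 112 | SE, all 112 | mn, one fold | SD, one fold |
|---|---|---|---|---|
| 20% | 22 × 90 = 1980 | 0.052 | 2.2 × 9.0 = 19.8 | 0.173 |
| 30% | 34 × 78 = 2652 | 0.045 | 3.4 × 7.8 = 26.5 | 0.150 |
| 50% | 56 × 56 = 3136 | 0.041 | 5.6 × 5.6 = 31.4 | 0.138 |

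A simulation of 3,000 runs per prevalence, using a score that never changes, agrees. The average between-fold SD is about 0.17, 0.15 and 0.13, and its ratio to the 112-patient SE is 3.2 to 3.3.

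**Step 3, can the SD reveal instability?** Suppose refitting made the true AUC vary between folds with an SD of 0.05 (assumed). At 30% prevalence the total would be √(0.150² + 0.05²) = 0.158 instead of 0.150. An SD from ten values has a relative error of roughly 1/√(2×9) = 24%, or about 0.035 here, so the difference cannot be seen. The SD also moves with the level of the AUC. A fixed score with AUC 0.95 gives 0.068 and 0.062 at 30% and 50% prevalence. A smaller SD may therefore only mean a higher AUC.

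**Step 4, the missing precision.** At AUC 0.80 the 95% half-widths from 112 patients would be 1.96 × 0.052 = 0.10, 1.96 × 0.045 = 0.09 and 1.96 × 0.041 = 0.08. For PPV at 50% prevalence, with sensitivity 0.85 and specificity 0.90 assumed, a fold with 5 of 6 correct has a Wilson interval of 0.44 to 0.97. The pooled 50 of 56 gives 0.79 to 0.95.

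**Step 5, folds with no predicted positive.** These use the same AUC 0.80 score. 'Unweighted' means a cut at 0.5 calibrated risk. 'Balanced' means a cut equivalent to full class balancing, as a stand-in for the weighted loss and oversampling in Section 9.4.2.

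- 20%, unweighted: about 3.5 of 10 folds have no PPV. The fold-mean PPV is 0.43 if those folds score 0 and 0.66 to 0.67 if they are dropped, against 0.65 pooled. F1 is 0.32 against 0.38 pooled.
- 20%, balanced: about 0.04 such folds per run. PPV is 0.42 against 0.39 pooled, and F1 is 0.51 against 0.51.
- 30%: about 45% of runs have at least one such fold if unweighted, and 1% if balanced.
- 50%: under 1% of runs.

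NPV is undefined in under 0.1% of cases at prevalences up to 50%, and in about 2% at 80%. F1 in count form, 2TP/(2TP+FP+FN), is always defined when a fold contains a positive. Stratification ensures that once there are at least ten positives.

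**The case against.** Averaging over folds is ordinary cross-validation practice, and the plan never calls the SD an error bar. A reader might infer that the plan reports an error bar three times too wide. The documents do not support that. The factor of about three is essentially √10, the gap between an SD and a standard error, and against a 95% half-width it is only about 1.6. This part of the objection stands. It does not rescue the SD, because Steps 2 and 3 show that it fails at the purpose the plan does give it.

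A reader might also infer that PPV, NPV and F1 will often be undefined or biased downward. That does not hold either. It needs an uncommon outcome and a model whose predictions stay unbalanced despite Section 9.4.2. The direction for PPV depends on a convention that the plan does not state. NPV and F1 are hardly affected once predictions are balanced.

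Nor do Sections 9.4.3 and 9.6 contradict each other on DeLong. The test needs paired patient-level predictions, and out-of-fold predictions could supply them. The plan does not say which predictions are used.

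The fixed-score check cannot show what share of the SD in the real study would come from refitting on about 101 patients. It shows only how much arises with no refitting at all. Finally, Section 7.2 lists the model metrics as secondary outcomes, the model hypothesis is secondary, and Section 6.3 says predictions do not guide surgery. That lowers the urgency, although Section 3.1 still names model validation as a primary objective.

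**Conclusion.** The point holds in a limited form. With about 11 patients per test fold, the between-fold SD of the AUC is about 0.13 to 0.17 for a model that does not vary at all, roughly three times the standard error from all 112 patients. It therefore measures neither stability nor precision, and no interval is planned that would supply the precision. This is so at all three prevalences examined, including the 50% planning value. The figures rest on an assumed AUC of 0.80, normally distributed scores and a fixed model. At AUC 0.95 the SDs are smaller but the ratio is much the same.

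The missing rule for undefined fold values and the unstated input to DeLong are minor gaps. Overall this should be fixed as a cheap improvement to the analysis plan. It does not invalidate the design.

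**What to change.** Amend Sections 9.4.3, 9.5 and 9.6 as follows.

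- Keep the 10-fold cross-validation and save each patient's out-of-fold predicted risk.
- Compute every metric, the calibration curve and the decision curve once on the 112 out-of-fold predictions. Give 95% intervals by patient-level bootstrap, or by Wilson for simple proportions.
- State that DeLong uses those same predictions.
- Set any classification cut-off inside the training folds.
- Assess stability by repeating the cross-validation over different random splits, for example 20, instead of by the between-fold SD.
- Report the fold-mean AUC alongside as a check. If any other fold-level metric is shown, state how undefined values are handled.

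No new patients or data are needed. The cost is wording and computing time: nine architectures, two outcomes and ten folds are 9 × 2 × 10 = 180 fits, and 20 repeats make 3,600. There are two statistical drawbacks. Pooling mixes ten slightly differently scaled models, which the fold-mean AUC helps to check. The bootstrap also leaves out refitting variance, so its intervals may be somewhat narrow, and the report should say so. Dividing the between-fold SD by √10 is not a safe substitute, because the training sets overlap.

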### 9.5 Model Performance Metrics

The following metrics will be calculated for each model:

- Area Under the ROC Curve (AUC)
- Accuracy
- Sensitivity (Recall)
- Specificity
- Positive Predictive Value (Precision)
- Negative Predictive Value
- F1 Score
- False Positive Rate
- Lift
- Brier Score
- Kappa Coefficient
- Dice Coefficient

### 9.6 Model Comparison

- DeLong test for comparing AUC values between models
- Probability-based model ranking approach (PMRA)
- Win-probability heatmaps
- Wald test p-value comparisons
- Decision curve analysis for clinical utility
- Calibration curves for reliability assessment
- Learning curves for overfitting assessment

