## 3. STUDY OBJECTIVES AND HYPOTHESES

### 3.1 Primary Objectives

1. To compare the sentinel lymph node detection rate among three tracer methods: ICG alone, CNs alone, and ICG+CNs dual-tracer combination.
2. To evaluate and compare the diagnostic performance (sensitivity, specificity, PPV, NPV) of each tracer method for predicting central lymph node metastasis.
3. To develop and validate deep learning models using multimodal features (spatiotemporal video features + clinical variables) for predicting second-echelon lymph node metastasis (SeLNM) and non-sentinel lymph node metastasis (NsLNM).

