### 3.2 Secondary Objectives

- To identify the optimal deep learning architecture for lymph node metastasis prediction.
- To determine the most important predictive features using SHAP analysis.
- To assess the clinical utility of AI-assisted intraoperative decision support.
- To evaluate safety outcomes including surgical complications and tracer-related adverse events.

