### 9.3 Primary Outcome Analysis

#### 9.3.1 SLN Detection Rate Comparison

- Chi-square test or Fisher's exact test for comparison among groups
- 95% confidence intervals for detection rates
- Pairwise comparisons with Bonferroni correction

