## 9.4 Deep Learning Model Development

### 9.4.1 Model Architectures

Nine deep learning architectures will be developed and compared:

- Convolutional Neural Network (CNN)
- Long Short-Term Memory (LSTM)
- CNN + LSTM hybrid
- CNN + LSTM + Attention
- Transformer
- Crossformer
- 3D-CNN

- LSTM + Transformer hybrid
- LSTM + Crossformer hybrid

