## 9.9 Software

- Python (version 3.9.21) for deep learning
- PyTorch (version 2.0) for model development
- Scikit-learn (version 1.2.2) for preprocessing and evaluation
- SPSS (version 21.0) for traditional statistical analyses
- SHAP library for model interpretability
- Significance level:  $\alpha = 0.05$  (two-sided) for all tests

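### Section 9.6 compares nine architectures on two targets by DeLong test without naming a contrast or an adjustment, so chance differences between models can easily be reported as significant

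*Combined protocol and SAP*

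**What the plan says.** Section 9.4.1 states: "Nine deep learning architectures will be developed and compared". Section 3.1 sets the models two targets: "predicting second-echelon lymph node metastasis (SeLNM) and non-sentinel lymph node metastasis (NsLNM". Section 7.1.3 makes SeLNM the main target of the models, but no testing order or division of alpha follows from that. Section 3.2 gives the purpose of the comparison: "To identify the optimal deep learning architecture for lymph node metastasis prediction".

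For the comparison, Section 9.6 lists "DeLong test for comparing AUC values between models". In the same list are Wald p-values, a probability-based ranking, win-probability heatmaps, decision curves, calibration curves and learning curves. No reference architecture is named and no adjustment is given. Section 9.9 fixes alpha at 0.05, "two-sided) for all tests".

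The plan's only multiplicity correction is in Section 9.3.1, for the detection rates of the three tracer groups: "Pairwise comparisons with Bonferroni correction". Only the dual-tracer group, 112 patients, has video for the models (Section 4.2).

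**The concern.** The authors corrected for multiplicity where there are three pairs of tracers, but gave no rule where there may be 36 pairs of models on each of two targets. Followed as written, every between-model p-value below 0.05 can be called significant. Such a result could then be cited in support of the secondary objective of naming the best architecture, although the error rate behind it is not controlled.

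This is separate from the optimism in the AUC of a model chosen because it scored highest. The question here is how often the plan would declare a difference between two architectures when none exists.

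**Working it through.** The plan states no number of DeLong tests and no family-wise error rate, so there is no figure of its own to reproduce.

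**Inputs from the plan.** 9 architectures (9.4.1); 2 targets (3.1); alpha 0.05 two-sided (9.9); 112 patients with video (4.2).

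**Assumptions, because the plan gives no values.** All nine models have the same true AUC; AUC 0.7 to 0.9; prevalence of each target 0.15 to 0.5; between-model score correlation 0.2 to 0.9; one score per patient per model. Overlap of training sets across the ten cross-validation folds was not modelled.

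**Step 1, number of tests.** Pairs per target = 9 × 8 / 2 = 36. Two targets: 36 × 2 = 72. Expected false positives if all models are equal: 72 × 0.05 = 3.6. Dependence between tests does not change this expectation.

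**Step 2, chance of at least one false pair, one target.** Tests that share a model are dependent. For nine equally good, equally correlated models, some pair has p < 0.05 exactly when the studentized range of the nine exceeds 1.96 × √2 = 2.77. With infinite degrees of freedom that probability is 0.572.

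**Step 3, both targets.** If the targets are independent: 1 − (1 − 0.572)² = 0.82. With correlated AUC errors between targets it is 0.81 at r = 0.3, 0.78 at 0.5, 0.75 at 0.7, 0.68 at 0.9, and 0.57 if the targets behave identically.

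**Step 4, checks by simulation.**

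| Setting | One target | Two independent targets |
|---|---|---|
| Actual DeLong tests, n = 100–112, 8 scenarios of 1,500 runs | 0.53–0.60 | 0.79–0.84 |
| Models in correlated clusters, 6 structures | 0.43–0.55 | 0.67–0.79 |
| One fixed reference against eight others (16 tests) | 0.25 | 0.44 |

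The last row follows from 1 − (1 − 0.249)² = 0.436.

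**Step 5, a different event.** Under the same null, the chance that the top model significantly beats all eight others is about 0.001 per target.

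**Step 6, effect of correction under the global null.** Here Holm and Bonferroni have the same chance of any rejection, because Holm's first step is the Bonferroni threshold.
- Over 72 tests: 0.05/72 = 0.00069, critical value 3.392, chance 0.020 per target; over both, 1 − (1 − 0.020)² ≈ 0.04.
- Within each target: 0.05/36 = 0.00139, critical value 3.197, chance 0.037 per target; over both, 1 − (1 − 0.037)² ≈ 0.07.

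**Step 7, cost in sensitivity.** Simulated standard errors of an AUC difference were 0.021 to 0.047 (n = 112, AUC 0.80, prevalence 30–50%, score correlation 0.5–0.9). Detectable difference at 80% power = (critical value + 0.842) × SE.
- Uncorrected: 2.80 × 0.021 to 2.80 × 0.047 = 0.06 to 0.13.
- Strictest step of a 36-pair correction: 4.04 × SE = 0.085 to 0.19.
- Strictest step for 72: 4.23 × SE = 0.09 to 0.20.

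**The case against.** The strongest reply is that all-pairs testing is inferred. Section 9.6 says only that models are compared with each other, whereas Section 9.3.1 says pairwise when it means pairwise. With one reference against eight others, the risk falls below one half. This stands as a limit on the figures. But the plan names no reference, so all pairs is the natural reading, and even the narrower reading gives five to nine times the nominal 0.05.

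Second, the equal-correlation model is idealised. Five of the nine architectures contain an LSTM, so clusters are realistic, and most clustered structures put a single target slightly below one half. Both targets are also measured in the same patients, and second-echelon nodes are themselves non-sentinel nodes, so independence of the targets is the upper end. If models cluster tightly and the targets behave almost identically, the combined risk could also fall below one half. This stands too, but none of it brings the risk near 0.05.

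Third, DeLong is one of several comparison tools, Section 9.5 lists twelve metrics, and no section makes p < 0.05 the rule for choosing a model. A reader might infer that the plan will probably crown a false winner. The documents do not support that: one chance pair does not identify an optimal architecture, and Step 5 shows that a clean sweep by chance is very rare.

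Fourth, Section 9.9 does not forbid adjustment, since the same line also covers the Bonferroni-corrected comparisons of 9.3.1. That is correct: the gap is the silence of 9.6.

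Finally, the stakes are modest. The objective is secondary, and Section 6.3 keeps the predictions out of surgical decisions. That limits the importance of the point, but the plan does not label these tests exploratory.

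**Conclusion.** The gap is real, and closing it is a cheap improvement. Read as all pairs, with nine equally good models, the plan carries a chance of about 0.57 per target (0.43 to 0.60 over the structures tried) of at least one false significant pair, and about 0.7 to 0.8 over both targets in most structures tried. Read as one reference against eight, it is about 0.25 and 0.44. AUC, prevalence and correlation are assumptions, and cross-validation dependence was not modelled. The omission itself is certain; the figures are conditional.

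Two stronger statements should not be drawn from this. Treating the 72 tests as independent gives 1 − 0.95^72 = 0.975, which overstates the risk because the tests share models and patients. Nor does it follow that most between-model claims from 112 patients would be noise: that depends on the true differences between architectures, and every calculation here assumes that there are none.

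**What to change.** In Section 9.6, choose one of two rules.

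- Prespecify one contrast per target, tested in fixed order with SeLNM first, in line with its status in Section 7.1.3, and NsLNM tested formally only if the SeLNM contrast is significant. Label all other between-model p-values, including the Wald comparisons, as descriptive.
- Or test all pairs with Holm across all 72 comparisons, which holds the overall chance of a false difference at about 0.04 under the global null. Holm within each target leaves about 0.07 over both, so it does not hold 0.05 for the family of 72.

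In Section 9.9, add after the significance level: *adjusted as stated in 9.3.1 and 9.6*. Rewording the objective in Section 3.2 is a matter of preference and is not needed.

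The change costs SAP wording only, with no new patients, data or procedures. The downside is lost sensitivity. On the assumed standard errors, the AUC difference detectable with 80% power rises from about 0.06–0.13 uncorrected to about 0.085–0.19 at the strictest step of a 36-pair correction, and slightly more for 72. The single-contrast rule avoids most of that loss, but allows a formal claim for only one comparison per target.

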## 9.7 Model Interpretability (SHAP Analysis)

SHapley Additive exPlanations (SHAP) will be used to:

- Calculate feature importance scores
- Generate summary plots (bar charts, beeswarm plots)
- Perform cluster analysis of feature contributions
- Create decision plots for individual predictions
- Identify key predictive features for clinical interpretation

## 9.8 Missing Data Handling

- Complete case analysis for primary outcomes
- Multiple imputation for secondary analyses if missing data >5%
- Sensitivity analyses to assess impact of missing data

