### 6.3 Surgical Procedure

All participants will undergo standard thyroid surgery following institutional protocols:

- Identification and separate submission of sentinel lymph node for pathological examination
- Ipsilateral thyroid lobectomy or total thyroidectomy as clinically indicated
- Ipsilateral central lymph node dissection (Level VI)
- Intraoperative frozen section analysis of sentinel lymph node

- Extended dissection (lateral compartment, contralateral central) based on frozen section findings

Surgical decisions will follow standard protocols and will NOT be influenced by deep learning predictions (which are performed retrospectively).

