## 7. OUTCOME MEASURES

### 7.1 Primary Outcomes

#### 7.1.1 Sentinel Lymph Node Detection Rate

Definition: Proportion of participants with successfully identified sentinel lymph nodes using each tracer method.

Measurement: Number with identified SLN / Total number in group  $\times 100\%$

Time Frame: Intraoperative (Day 0)

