#### 7.1.2 Sentinel Lymph Node Metastasis (SLNM) Status

Definition: Presence or absence of cancer metastasis in the sentinel lymph node.

Classification: Positive (macrometastasis or micrometastasis) or Negative

Gold Standard: Final histopathological examination (paraffin section)

Time Frame: Within 7 days after surgery

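### Sections 9.3.2 and 9.8 give no rule for participants in whom no sentinel node is found, so tracer accuracy may be estimated only on subsets that the tracer helps select

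*Combined protocol and SAP*

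**What the plan says.** Section 3.1 makes it a primary objective to evaluate and compare the "diagnostic performance (sensitivity, specificity, PPV, NPV) of each tracer method for predicting central lymph node metastasis". The test result is SLN metastasis status, defined in Section 7.1.2 as "Presence or absence of cancer metastasis in the sentinel lymph node" and classed as "Positive (macrometastasis or micrometastasis) or Negative". There is no category for a node that was not found.

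Section 9.3.2, under the primary outcome analysis, gives formulas for sensitivity, specificity, PPV and NPV. It does not say which participants fill each cell or who is in the denominator. Section 7.2 lists the same four measures as secondary outcomes.

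Section 9.8 has three lines: "Complete case analysis for primary outcomes"; "Multiple imputation for secondary analyses if missing data >5" per cent; and "Sensitivity analyses to assess impact of missing data". None mentions failed mapping.

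Three other places bear on the point. The detection rate in Section 7.1.1 is "Number with identified SLN / Total number in group", so failed mappings count there. Section 6.3 plans a Level VI dissection on the tumour side for all participants, and Section 5.2 requires a scheduled central dissection for entry. Section 3.3 hypothesises that the dual tracer detects sentinel nodes more often than either tracer alone.

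**The concern.** A participant with no sentinel node found has a known central nodal status but no test result. The plan does not say what happens to that participant in the accuracy tables.

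- **If complete case governs**, the participant is dropped. Sensitivity and NPV then describe only patients in whom mapping worked, which is an event after injection that the study expects the tracer to influence.
- **If the secondary label governs**, multiple imputation could assign a status to a node that was never identified. Those values would be drawn from participants in whom mapping succeeded.

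Neither answers Objective 2, which asks how well the method as used predicts central metastasis. A node-positive patient whose mapping failed was not identified by the method. Leaving the rule open also means that the choice could be made after the data are seen. Restricting to detected participants also departs from the ITT definition in Section 9.1, which covers everyone who received the assigned injection.

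**Working it through.** **Inputs from the documents (Sections 4.2 and 5.4).** 112 per group; prevalence of nodal metastasis 50%, so 112 × 0.50 = 56 node-positive per group; expected sensitivity 85% (dual) and 50% (single); expected specificity 90%.

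**Assumptions.** The documents give no expected detection rate D, so a range is shown. Detection is taken as independent of nodal status. Section 5.4 does not say whether 85% and 50% are conditional on detection; they are first read as conditional.

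**Sensitivity.** Let s be sensitivity among detected participants. Detected-only sensitivity is s. Among all injected participants, with non-detection counted as test-negative, it is D × s. For example, 0.95 × 0.85 = 0.8075 and 0.80 × 0.85 = 0.68.

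| Detection, dual / single | Sensitivity among detected, dual / single | All injected, dual vs single | Difference in points, detected-only → all injected |
|---|---|---|---|
| 100% / 100% | 85% / 50% | 85.0% vs 50.0% | 35 → 35 |
| 95% / 90% | 85% / 85% | 80.8% vs 76.5% | 0 → 4.3 |
| 95% / 80% | 85% / 85% | 80.8% vs 68.0% | 0 → 12.8 |
| 95% / 70% | 85% / 85% | 80.8% vs 59.5% | 0 → 21.3 |
| 95% / 90% | 85% / 50% | 80.8% vs 45.0% | 35 → 35.8 |
| 95% / 80% | 85% / 50% | 80.8% vs 40.0% | 35 → 40.8 |
| 95% / 70% | 85% / 50% | 80.8% vs 35.0% | 35 → 45.8 |
| 90% / 90% | 85% / 50% | 76.5% vs 45.0% | 35 → 31.5 |

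The first row returns the plan's own figures: with complete detection the issue vanishes.

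**Participants lost.** At 95% versus 80% detection, the detected-only tables hold 56 × 0.95 = 53.2 and 56 × 0.80 = 44.8 expected node-positive participants, instead of 56 in each group.

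**Direction.** Dropping non-detections raises a group's sensitivity by s × (1 − D). With 85% and 50%, and dual detection of 95%, the dual group gains 0.85 × 0.05 = 4.25 points and the single group 0.50 × (1 − D). These are equal when 1 − D = 0.085, so D = 91.5%. Below that, conditioning understates the dual tracer's advantage; above it, conditioning overstates it.

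**If 85% and 50% are all-injected values.** At 95% versus 80% detection the detected-only figures are 0.85 / 0.95 = 89.5% and 0.50 / 0.80 = 62.5%. The 35-point difference would then appear as 27.0.

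**NPV.** At 50% prevalence with no false positives (an assumption), NPV = 1 / (2 − sensitivity). With s = 85% in both groups, detected-only NPV is 1 / 1.15 = 87.0% in each. At 95% versus 80% detection the all-injected values are 1 / 1.1925 = 83.9% and 1 / 1.32 = 75.8%.

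With the plan's 90% specificity, all-injected specificity is 1 − 0.10 × D, so 90.5% and 92.0%. NPV goes from 0.90 / (0.90 + 0.15) = 85.7% in both groups to 0.905 / (0.905 + 0.1925) = 82.5% and 0.92 / (0.92 + 0.32) = 74.2%.

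**The case against.** The strongest reply is that the plan nowhere says these participants are dropped. A reader might infer from Section 9.8 that exclusion is the written rule. It is not: Section 9.8 is silent on failed mapping, the cells in Section 9.3.2 are undefined, and coding non-detection as test-negative would also fit the text. That stands, so the defect is a missing rule, with exclusion as its most natural reading.

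Second, Section 7.2 calls these measures secondary, so complete case may not apply. This also stands, but imputation is no remedy, and the conflict with Sections 3.1 and 9.3 is itself unresolved. The sensitivity analyses in Section 9.8 have no stated content and do not settle the main estimate.

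Third, failed mapping is not hidden from the trial, because the detection rate is a primary outcome on the whole group with pairwise comparisons. Reporting detection and conditional accuracy separately is a legitimate choice of estimand. That is fair, and it is why both versions should be shown. But the plan does not declare that choice, and the conditional figures alone do not answer Objective 2 as worded. Section 9.3.2 names no between-tracer test, so the comparison comes from the objective.

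Two further readings are tempting. One is that a true difference of about 13 points would be reported as none. That needs equal 85% sensitivity among detected participants, which is not what Section 5.4 expects; with 85% and 50% read as conditional, the shift at the same detection rates is 5.75 points. The other is that conditioning always favours the weaker tracer. The equal-detection case shows that it does not.

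**Conclusion.** The point holds as an omission. The plan has no rule for non-detection in the accuracy analysis and does not define the cells. Both of its missing-data rules, applied to these participants, would base Objective 2 on, or impute it from, subsets shaped by the tracer.

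The size cannot be fixed from the documents. For dual detection of 95% and single detection of 70% to 90%, the between-tracer difference in sensitivity shifts by 4.3 to 21.3 points if sensitivity among detected participants is equal at 85%. It shifts by 0.8 to 10.8 points if the plan's 85% and 50% are conditional values. These figures assume detection independent of nodal status; if it is not, the size could differ. The direction depends on the detection rates, though a large detection advantage for the dual tracer would lead the detected-only comparison to understate its benefit. The detection-rate endpoint is unaffected. This should be corrected because the remedy is cheap and needs no new data.

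**What to change.** 1. In Section 9.3.2, define all four cells against the central dissection result. Report sensitivity, specificity, PPV and NPV for all injected participants who had central dissection, counting non-detection as test-negative: false negative if node-positive, true negative if node-negative.
2. Report beside it the version restricted to participants with a sentinel node found. Both are needed, because counting node-negative failures as true negatives raises specificity slightly.
3. In Section 9.8, state that non-detection is an outcome, not missing data to be dropped or imputed.
4. Reconcile the status of diagnostic performance between Sections 3.1, 7.2 and 9.3.

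The cost is SAP wording, one extra table and somewhat lower reported sensitivities. No new data are required.
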